## **1. INTRODUCTION**

### **1.1 Background and rationale for conducting this study**

#### **1.1.1 Background**

Asthma is a syndrome characterized by airway inflammation, reversible airway obstruction and airway hyperresponsiveness. Patients present clinically with recurrent wheezing, shortness of breath, cough and chest tightness. Asthma is a leading cause of morbidity with a global prevalence of approximately 300 million; it is estimated that the number of people with asthma may increase to 400 - 450 million people worldwide by 2025 (Masoli et al 2004).

The current approach to anti-inflammatory controller therapy in asthma is based on a step-wise intensification of a daily maintenance regimen primarily centred around inhaled

corticosteroids (ICS) and leukotriene receptor antagonists (LTRA), with the addition of long-acting  $\beta_2$  agonists (LABA) in patients with more severe asthma (Global Initiative for Asthma (GINA 2014, NAEPP 2007). Despite treatment per management guidelines, up to 50% of patients have asthma that is not well-controlled (Bateman et al 2010). This results in considerable impact on quality of life, disproportionate use of healthcare resources, and adverse reactions from regular systemic steroid use. Symptom control in children and adolescents with asthma can be similarly challenging, due in part to the limitations of current therapeutic modalities. Longer treatment courses, over a period of months or years, and higher medication doses may be required to achieve the maximum possible improvement in lung function in children older than 5 years (GINA 2014). Therefore, there remains an unmet medical need for patients whose asthma is not controlled by existing therapies.

The observed variability in clinical response to currently available asthma therapies appears to be related, in part, to distinctive inflammatory phenotypes (Wenzel 2012). In particular, asthma associated with eosinophilic inflammation in the airway (often referred to as eosinophilic asthma) is common (approximately 40% to 60% of asthmatics) with the degree of eosinophilia associated with clinical severity including the risk of asthma exacerbations (Bateman et al 2010, Bousquet et al 1990, Louis et al 2000, Di Franco et al 2003, Scott and Wardlaw 2006, Simpson et al 2006, Zhang and Wenzel 2007). Adjusting conventional ICS-based asthma therapy according to the degree of elevated sputum eosinophils as a marker of disease activity resulted in a reduction in the frequency of asthma exacerbations in prospective trials (Green et al 2002, Jayaram et al 2006). Interleukin-5 (IL-5) is a cytokine factor essential for eosinophil trafficking and survival (Molfinio et al 2011). Clinical trials of neutralizing anti-IL-5 antibodies (mepolizumab and reslizumab) in patients with uncontrolled eosinophilic asthma resulted in an improvement in key asthma control metrics, including asthma exacerbations (Castro et al 2011, Pavord et al 2012). These promising results support continued development of therapies targeting the IL-5 pathway in eosinophilic asthmatics unresponsive to standard therapies.

In contrast to anti-IL-5 therapies, benralizumab (MEDI-563) is a humanized, afucosylated, monoclonal antibody that binds specifically to the human IL-5 receptor alpha subunit (IL-5R $\alpha$ ) on the target cell. The IL-5 receptor (IL-5R) is expressed almost exclusively on the surface of eosinophils and basophils (Takatsu et al 1994, Toba et al 1999). Afucosylation confers enhanced antibody-dependent cellular cytotoxicity (ADCC) which results in highly efficient eosinophil depletion by apoptosis (Kolbeck et al 2012). Single and repeated doses of benralizumab in mild to severe asthma patients during early development or Phase 1/2 development resulted in depletion of blood and airway eosinophils, and improvement in multiple metrics of asthma control including asthma exacerbations, lung function, and Asthma Control Questionnaire (ACQ-6) scores (Busse et al 2010, Gossage et al 2012, Molfinio et al

2012, and Phase 2b MI-CP220 study). For further details please refer to the Investigator's Brochure (IB).

### **1.1.2 Rationale for conducting this study**

The treatment options for patients who remain uncontrolled by ICS-LABA are extremely limited. In previous clinical studies, benralizumab administration resulted in rapid and prolonged depletion of eosinophils in the peripheral blood and in the asthmatic airway with associated improvements in multiple metrics of asthma control. The magnitude of clinical improvement was positively correlated with baseline blood eosinophil counts and was most consistently observed in patients with absolute blood eosinophil counts  $\geq 300/\mu\text{L}$ . In the pivotal studies (Bleecker et al 2016, FitzGerald et al), compared with placebo, benralizumab 30 mg administered subcutaneously (benralizumab 30 mg every 4 weeks for the first 3 doses and then every 8 weeks thereafter) significantly reduced the annual asthma exacerbation rate, improved asthma symptom and lung function (pre-bronchodilator FEV1). The purpose of this trial is to confirm the efficacy and safety of benralizumab administration in asthma patients who are otherwise uncontrolled on current standard of care therapy. The question of the baseline blood eosinophil level that predictably ensures the clinical benefit in patients will also be addressed in the study by inclusion of patients with blood eosinophil counts  $\geq 300/\mu\text{L}$  and  $< 300/\mu\text{L}$ .

## **1.2 Rationale for study design, doses and control groups**

This is a regional study designed to investigate the safety and efficacy of the fixed dose benralizumab (30 mg) administered subcutaneously (SC) every 4 weeks for the first 3 doses and then every 8 weeks thereafter in exacerbation-prone asthma patients who remain uncontrolled on medium to high-doses ICS-LABA with or without oral corticosteroids and other asthma controller(s).

Primary efficacy will be determined based on reduction in the rate of asthma exacerbations over 48 weeks for benralizumab versus placebo. In order to avoid biasing the results, the study will be randomised and double-blinded with stratification by age group (adult or adolescent), country/region and eosinophil category ( $\geq 300/\mu\text{L}/< 300/\mu\text{L}$ ).

The study will randomise patients with screening blood eosinophils  $\geq 300/\mu\text{L}$  and  $< 300/\mu\text{L}$  at a ratio of about 2:1. The 2:1 stratification of patients with eosinophil counts  $\geq 300/\mu\text{L}$  and  $< 300/\mu\text{L}$  is intended as a means of enriching the population for patients most likely to respond to benralizumab (ie,  $\geq 300/\mu\text{L}$ ), while still accommodating patients below this threshold in order to help understand where additional benefit drops off.

The benralizumab dose (30 mg SC, fixed) and the maintenance regimens are based on all available safety, efficacy and immunogenicity data, as well as population exposure-response modeling, and stochastic trial simulations from earlier phase benralizumab trials. In particular, Phase 2b MI-CP220 study (Castro et al 2014) showed that fixed doses of

benralizumab  $\geq 20$  mg administered every 8 weeks were clinically effective. The potential impact on efficacy of anti-drug antibodies and body weight on pharmacokinetics (PK) were incorporated in a population PK model. Analyses of efficacy endpoints (asthma exacerbations, forced expiratory volume in 1 second [FEV1] and ACQ) suggest 30 mg every 8 weeks (with the first 3 doses administered every 4 weeks) is an effective and tolerable dose for further testing in patients with severe asthma. This dose corresponds to the ED90 (benralizumab dose corresponding to 90% of maximum efficacy) for asthma exacerbation reduction and ACQ, and maintains a steady-state PK exposure close to EC90 (benralizumab serum concentration corresponding to 90% of maximum efficacy) levels for FEV1 and ACQ. Asthma manifestations and responses to existing treatments in adolescents and adults are similar. With a 40 kg lower body weight limit, the projected PK exposure in adolescents mostly overlaps with that in adults. The PK difference between adolescents and adults is expected to be small and within the normal range of between-patient variability among adults. Further, the 100 mg Q8W top dose investigated in Phase 2b study provided adequate exposure coverage. To date, there are no data suggesting a dose- or exposure-related increase in treatment-emergent adverse events (TEAEs) with benralizumab in adult patients. As such, adolescent patients ( $\geq 40$ kg) will receive the 30 mg adult dose in Phase 3 studies.

Other stable asthma therapies on top of ICS-LABA that are within expert guidance and that are not restricted per protocol (see Section 3.8) are allowed in order to accommodate local standards of care.

### 1.3 Benefit/risk and ethical assessment

There are few treatment options for patients whose asthma remains uncontrolled on medium to high-dose ICS-LABA (GINA 2014). The evidence base for oral add-on therapies (ie, oral corticosteroids, leukotriene inhibitors, and xanthenes) is extremely limited. Anti-IgE therapy (ie, omalizumab) may improve control in patients with severe asthma and IgE-mediated allergy to a perennial allergen. Tiotropium is a long-acting bronchodilator that has recently been shown to produce improvement in lung function and exacerbation risk (pooled data) in patients with severe asthma, with inconsistent effects on other measures of asthma control (Kerstjens et al 2012). As such, new therapies are needed for asthma management in patients who remain uncontrolled on standard of care.

In adult patients whose asthma was poorly controlled on medium-to-high dose ICS-LABA benralizumab, at fixed doses of  $\geq 20$  mg, produced improvements in multiple metrics of asthma control including the annual rate of asthma exacerbations, lung function, ACQ-6 scores, and symptoms (Castro et al 2014). These findings have subsequently been confirmed in two large Phase 3 studies (Bleecker et al 2016, FitzGerald et al) where a fixed dose of 30 mg was given either every 4 weeks or every 8 weeks. Clinical benefit appeared to be greatest in patients with blood eosinophil counts  $\geq 300/\mu\text{L}$ . The blood eosinophil count below which

benralizumab is generally not effective remains unclear at this point in time, and will be explored in this study.

Development of anti-drug antibodies (ADA) to benralizumab has been documented. Theoretical risks of developing ADA include decreased drug efficacy and hypersensitivity reactions (e.g., anaphylaxis or immune complex disease). There was no apparent impact of ADA on overall benralizumab safety or efficacy in the previous Phase 3 studies in asthma. Serious hypersensitivity reactions (including anaphylaxis) are an identified risk of biologic therapy, including benralizumab. Anaphylaxis may be life-threatening. Risk minimization includes observation in line with clinical practice at the clinical site following IP administration for the appearance of any acute drug reactions.

Eosinophils are a prominent feature of the inflammatory response to helminthic parasitic infections, and the presence of infiltrating eosinophils has been circumstantially associated with a positive prognosis in certain solid tumors. Therefore, there is a theoretical risk that prolonged eosinophil depletion may diminish the ability to defend against helminthic parasites, or negatively impact the natural history of certain malignant tumors. Risk minimization measures include exclusion of patients with untreated parasitic infection and active or recent malignancy, in conjunction with the performance of routine pharmacovigilance activities.

The efficacy and safety data obtained to date support the continued clinical development of benralizumab in asthma.

A detailed assessment of the overall risk/benefit of benralizumab in patients with asthma is given in the Investigator's Brochure (IB).

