### **3.2 Exclusion criteria**

Patients should not enter the study if any of the following exclusion criteria are fulfilled:

- 1 Known history of clinically important pulmonary disease other than asthma (e.g., active lung infection, Chronic obstructive pulmonary disease (COPD), bronchiectasis, pulmonary fibrosis, cystic fibrosis, hypoventilation syndrome associated with obesity, lung cancer, alpha 1 anti-trypsin deficiency, and primary ciliary dyskinesia) or ever been diagnosed with pulmonary or systemic disease, other than asthma, that are associated with elevated peripheral eosinophil counts (e.g., allergic bronchopulmonary aspergillosis/mycosis, Churg-Strauss syndrome, hypereosinophilic syndrome).
- 2 Known history of any disorder, including, but not limited to, cardiovascular, gastrointestinal, hepatic, renal, neurological, musculoskeletal, infectious, endocrine, metabolic, haematological, psychiatric, or major physical impairment that is not stable in the opinion of the Investigator and could:
  - Affect the safety of the patient throughout the study
  - Influence the findings of the studies or their interpretations
  - Impede the patient's ability to complete the entire duration of study.
- 3 Known history of allergy or reaction to the investigational product (IP) formulation.

- 4 Known history of anaphylaxis to any biologic therapy.
- 5 A helminth parasitic infection diagnosed within 24 weeks prior to the date informed consent, and assent when applicable, is obtained that has not been treated with, or has failed to respond to standard of care therapy.
- 6 Acute upper or lower respiratory infections requiring antibiotics or antiviral medication within 30 days prior to the date informed consent, and assent when applicable, is obtained or during the screening period.
- 7 Any clinically significant abnormal findings in physical examination, vital signs, haematology, clinical chemistry, or urinalysis during screening period, which in the opinion of the Investigator, may put the patient at risk because of his/her participation in the study, or may influence the results of the study, or the patient's ability to complete entire duration of the study.

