## **3.9 Discontinuation of investigational product**

Patients may be discontinued from investigational product (IP) in the following situations:

- 1 Patient decision. Patients are free to discontinue treatment at any time, without prejudice to further treatment (see Section 3.10).
- 2 Adverse event (AE) that, in the opinion of the Investigator or AstraZeneca, contraindicates further dosing.
- 3 Risk to patient as judged by the Investigator or AstraZeneca.
- 4 Severe non-compliance to study protocol.
- 5 Eligibility requirement found not to be fulfilled (see section 3.4).
- 6 Pregnancy.
- 7 Lost to follow-up.
- 8 Development of any study specific criteria for discontinuation:
  - Anaphylactic reaction to the IP requiring administration of epinephrine.
  - Development of helminth parasitic infestations requiring hospitalization.
  - An asthma-related event requiring mechanical ventilation.

If a patient misses more than 2 doses of IP at any time within a calendar year, it is strongly recommended that a conversation between the investigator and AZ study physician takes place to review the patient's adherence to treatment and decide on further patient's disposition.

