Visit 3 can be performed within 1 week before Visit 4. Visit 3 and Visit 4 may take place on the same day only for well characterized patients (those who did not have lab results outside the normal range at Visit 1 for parameters associated with eligibility criteria (e.g. Liver Function Tests)) as any such results should be retested, with results available before randomisation, in order to ensure patient eligibility is not affected. On Visit 4 ACQ-6 will be recorded (for baseline purposes only). Patient's eligibility should be evaluated at each visit during the run-in period with the relevant documentation entered in the source and eCRF.

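### Exclusion criterion 5 bars untreated helminth infection only if it was diagnosed in the 24 weeks before consent; older untreated infections, and those first found during screening, are left to Investigator judgement

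*Supplement*

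**What the plan says.** Section 1.3 (Benefit/risk and ethical assessment) explains that prolonged eosinophil depletion could, in theory, weaken defence against helminths. It then states the safeguard: "Risk minimization measures include exclusion of patients with untreated parasitic infection and active or recent malignancy". No time window is attached.

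Section 3.2 turns this into exclusion criterion 5. The criterion has two conditions, and both must hold. The first is a window on the date of diagnosis: "A helminth parasitic infection diagnosed within 24 weeks prior to the date informed consent". The second is treatment status: the infection "has not been treated with, or has failed to respond to standard of care therapy".

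The next criterion, number 6 (acute respiratory infection needing antibiotics or antivirals), sets its window differently. It counts 30 days back from the date consent "is obtained or during the screening period", so it runs on past consent.

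Two general criteria in the same section could also reach a helminth infection. Criterion 2 covers a known disorder, infectious disorders included, "that is not stable in the opinion of the Investigator and could" affect safety, the findings or completion of the study. Criterion 7 covers clinically significant abnormal screening findings "which in the opinion of the Investigator, may put the patient at risk" or may affect the results or completion of the study.

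After randomisation, the only helminth-specific rule is a discontinuation criterion in Section 3.9: "Development of helminth parasitic infestations requiring hospitalization".

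**The concern.** On the protocol's own rationale, what matters is whether an infection is still untreated when an eosinophil-depleting drug is given. The date on which it was diagnosed does not bear on that. Criterion 5 makes the date decisive, so the mandatory rule is narrower than the safeguard that the benefit/risk section relies on.

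The stake is individual patient safety. A patient outside the rule can be randomised 1:1 and, if allocated to benralizumab, be dosed for most of a year unless an Investigator chooses to act. The specific stopping rule helps little: it speaks of an infestation that develops and is serious enough for admission. Any earlier stop again depends on the judgement of the Investigator or the sponsor. Entry is therefore where the safeguard has to work.

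**Working it through.** There is no plan figure to reproduce. The check is to run each kind of patient through criterion 5, and then to look for any other rule that would exclude those it misses.

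**Scope of criterion 5**

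| Helminth infection | Excluded by criterion 5? |
|---|---|
| Diagnosed 24 weeks or less before consent, untreated or unresponsive | Yes |
| (a) Diagnosed more than 24 weeks before consent, still untreated or unresponsive | No |
| (b) First diagnosed between consent and randomisation, untreated or unresponsive | No |
| Treated, with response, whenever diagnosed | No, by intention |

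**Other rules that might catch (a) and (b)**

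- Criterion 1 bars anyone ever diagnosed with another disease associated with raised eosinophils. Its examples include no parasite. Reading it to cover helminths would also bar the successfully treated infections that criterion 5 admits and would make criterion 5 redundant, so it does not close the gap.
- Criterion 2 requires the disorder to be not stable, in the Investigator's opinion. An infection left untreated for over 24 weeks could be judged stable, so group (a) may escape it.
- Criterion 7 lists physical examination, vital signs, haematology, chemistry and urinalysis, again subject to opinion. A helminth diagnosis made outside the study by some other test is not on that list.
- Table 1 schedules hepatitis B and C serology at screening and no helminth test.

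No mandatory rule in Sections 3.1, 3.2, 3.8, 3.9 or 4.1 excludes group (a) or (b).

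**Length of the time outside the mandatory rule**

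- Look-back limit: 24 × 7 = 168 days. Every diagnosis earlier than that is uncovered.
- Consent to randomisation, Table 1: 28 to 42 days.
- With the extension for transient reasons in Section 4.1.3: 42 + 14 = 56 days.
- Shortened re-screen in Section 4.1.3 (Visits 1 and 2 on one day, Visit 3 a week later, Visit 4 a week after that): 7 + 7 = 14 days.
- After a screening exacerbation, Section 4.1.3.1 delays the next visit by at least 14 days from the end of systemic steroids, or from return to the baseline steroid dose. It states no maximum.

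These figures measure the window in the wording. They do not estimate risk.

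**Maximum exposure**

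Three doses four weeks apart, then one every eight weeks, with the last at Week 40, gives Weeks 0, 4, 8, 16, 24, 32 and 40: 7 doses.

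**The case against.** The literal reading is hard to dispute, so the case against is about consequence.

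- **Section 1.3 is a summary.** It compresses the malignancy rule in the same sentence, and it refers to the Investigator's Brochure for the full assessment, where a reason for the 24-week window may be given. This stands in part: the shorter wording is not a contradiction in itself. But criterion 13, which implements the malignancy half, admits patients on remission and time since curative therapy and does not use the date of diagnosis. The helminth half is the one tied to diagnosis date.
- **Criteria 2 and 7 already reach these patients, and opinion-based criteria are normal.** Criterion 8 treats ECG abnormalities in the same way. It is true that these criteria will catch some patients. They remain discretionary, with the limits set out above.
- **Section 7.4 defers dosing for an intercurrent illness that may compromise safety.** This is a further layer and could stop a first dose in group (b). It too depends on the Investigator's opinion.
- **Re-screened patients sign a new consent, which resets the window.** This is correct. An infection found in a first screening then falls within the 24 weeks, so the 14-day re-screen leaves uncovered only infections first diagnosed after re-consent. But criterion 5 does not force the first screen failure.
- **Almost nobody is affected, and the rewording detects no new infections.** This stands as to size. It is the reason for a low rating, but it does not make the criterion match its stated purpose.

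**Conclusion.** The concern holds. Criterion 5 is narrower than the safeguard in Section 1.3, and groups (a) and (b) are excluded only if an Investigator so judges.

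The effect is low. The documents give no count of affected patients. The number is assumed to be very small, because these infections must be known and untreated and because criteria 2 and 7 will remove some of them. The protocol describes the risk as theoretical, and no effect on the primary analysis is claimed. This is a modest safety improvement that the sponsor could make. It is not a flaw that threatens the trial's conclusions. Any justification for the 24-week limit in the Investigator's Brochure could not be seen.

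**What to change.** Reword exclusion criterion 5 so that it covers any known helminth parasitic infection, whenever diagnosed up to randomisation, that "has not been treated with, or has failed to respond to standard of care therapy". Infections that were treated and responded stay eligible, as now.

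The cost is one sentence in the next amendment. No test or visit is added: Section 4.1.2 already requires that "eligibility should be evaluated at each visit during the run-in period", and Table 2 repeats the inclusion and exclusion check at Visit 4. At most a few extra screen failures would follow, some of them avoidable by treating the infection first.
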